8.8.4 Screening failure

Screening will be based on patient's medical history and documented type 2B (cardio-inhibitory) response of the the VASIS classification⁽³⁾ during baseline TT, according to the Italian protocol.⁽⁷⁾

Type 2B TT response is defined as asystole occurring for more than 3 sec irrespective of BP fall.

Patients who will not meet these requirements in addition to the inclusion/exclusion criteria cannot be enrolled in the study. Screening will be documented in the Screening Log Sheet.

8.8.5 Drop-out criteria

8.8.5.1 Withdrawal of patient consent

Informed patient consent is voluntary and required from all patients. The patient can withdraw her or his consent at any time. If a patient withdraws her or his consent, the investigator should try to ascertain the reasons of withdrawal while fully respecting patient's rights.

If the health status of the patient does not allow further participation in the study the investigator will decide on early study termination. An early study termination or withdrawal will not affect the patient's future medical care in any way.

8.8.6 Point of enrolment and study termination

A subject is considered enrolled in the BIOSync CLS Study upon the signature of the Informed Consent Form.

Patients will terminate their study participation at the 24-month in-hospital follow-up or at the assessment of a primary endpoint event occurrence, whichever comes first.

8.8.7 Timelines

The study is planned to start in the second quarter of 2015 and will be probably completed in 2019. The enrolment period is expected to last 24 months and the planned duration of subject's participation is 2 years.

9 STUDY PROCEDURES

9.1 Overview

This section describes all the study-related procedures.

At enrolment, patients will receive anonymous syncope and pre-syncope assessment questionnaires to be self-administered upon each primary and secondary endpoint event experienced and mailed (by ordinary mail) to an external CRO every 3 months after discharge by using anonymous pre-paid and pre-addressed envelopes.

Furthermore, subsequent to the IPG implant and hospital discharge, patients will be visited in hospital at 12-, and 24-months. More frequent scheduled visits are optional and can be performed according to the site clinical practice. However, any scheduled or unscheduled in-hospital visit must be documented in the appropriate eCRF. Optionally, a 1-month (± 14 days) in-hospital visit may be performed to repeat the TT.

The follow-ups should take place within a certain time frame as listed in Table 1. This schedule should be followed as closely as possible. If circumstances prevent the presence of the patient at the follow-up visit, the reason for the missed follow-up has to be indicated on the eCRF.

9.1.1 Remote monitoring

Home Monitoring is highly recommended for remote control in order to optimize patient retention and reduce loss. It may be activated at any time throughout the study. It does not replace in-hospital visits for the purpose of this study.

[figure not shown]

Figure 1. Study flow-chart

FOR-137-014-A / SOP-137-020.020 / CRQ-13-00841

Table 2. Investigation schedule

| Investigations | Enrollment | Implantation /Discharge Month 0 | Month 1 ± 14 days in-hospital (optional) | Month 3 PSAQ* collection | Month 6 PSAQ collection | Month 9 PSAQ collection | Month 12 PSAQ collection; ±30 days in-hospital | Month 15 PSAQ collection | Month 18 PSAQ collection | Month 21 PSAQ collection | Month 24 PSAQ collection; ±30 days in-hospital |
|---|------------|---------------------------------|--|--------------------------|-------------------------|-------------------------|--|--------------------------|--------------------------|--------------------------|--|
| Patient informed consent | x | | | | | | | | | | |
| Verification of in- and exclusion criteria | x | | | | | | | | | | |
| Demographic data | x | | | | | | | | | | |
| ECG | x | | | | | | | | | | |
| Echo data (not older than 3 months) | x | | | | | | | | | | |
| Medical history | x | | | | | | | | | | |
| Co-morbidities | x | | | | | | | | | | |
| Cardiovascular medication | x | | | | | | x | | | | x |
| Tilt table test | x | | x | | | | | | | | |
| IPG implantation | | x | | | | | | | | | |
| Randomization | | x | | | | | | | | | |
| Device programming settings and diagnostics | | x | x | | | | x | | | | x |
| Primary endpoint assessment (syncope) by independent agency | | | | x | x | x | x | x | x | x | x |
| Pre-syncope assessment by independent agency | | | | x | x | x | x | x | x | x | x |
| Other secondary endpoint assessment | | | x | | | | | | | | |
| (S)AE, (S)ADE, DD | | x | x | x | x | x | x | x | x | x | x |

PSAQ= Patient self-administered questionnaire

This document contains confidential information and should be maintained in a secure location and should not be copied or made available for review by any unauthorized personnel.

9.2 Enrolment

If the patient meets all the inclusion criteria and no exclusion criterion, he/she will be asked to read and sign an Informed Consent Form. This will allow a detailed recording of data being evaluated during the study. The consenting process is described in detail in Section 17. A subject is considered enrolled in the BIOSync CLS Study upon signing the Informed Consent Form. The patient will be advised to avoid activities which may pose risks in case of transient loss of consciousness.

The baseline data may be collected the same day the consenting procedures are completed.

For baseline evaluation, the investigator collects the following data on an eCRF:

- Demographic characteristics
- Device therapy indication
- ECG diagnosis
- Number and type of previous ineffective therapies for reflex syncope
- Comorbidities
- Cardiomyopathies
- Arrhythmias
- Cardiovascular medication
- Baseline TT response which includes time of onset of pre-syncope (first symptoms), BP value at the time of onset of pre-syncope, occurrence and time of onset of syncope, type and duration of asystole, minimum BP.

Enrolments take place before IPG implantation.

9.3 Implantation

IPG implantation will be performed according to standard technique and will be conducted so as to ensure optimal pacemaker functioning with acceptable pacing, sensing, impedance values.

9.4 Pre-hospital discharge

After implant and prior to hospital discharge, the investigator shall query and obtain the patient randomization by accessing the dedicated web site. The IPGs will be programmed accordingly.

Programming details are reported in the following Table 3. Parameters which are not listed have to be intended freely selectable.

Table 3. Device programming recommendations

| Parameter | Active group | Control group |
|----------------------|---------------------|----------------------|
| Mode | DDD-CLS | OFF* |
| Basic rate Day/Night | 50 bpm/OFF | --- |

This document contains confidential information and should be maintained in a secure location and should not be copied or made available for review by any unauthorized personnel.

| | | |
|----------------------------|----------------|----------|
| Maximum CLS rate** | 120 bpm | --- |
| CLS response** | Medium | |
| CLS Resting rate control** | OFF | --- |
| Mode switching | OFF | --- |
| AV Delay | Low; 150-120ms | --- |
| AV hysteresis mode | IRSplus | |
| Atrial Overdrive Pacing | OFF | --- |
| PMT protection | ON | --- |
| IEGM recordings | | |
| High atrial rate | AT | AT |
| High ventricular rate | ON | ON |
| Patient triggering | OFF | OFF |
| Rates for statistics | | |
| HAR limit | 200 bpm | 200 bpm |
| HVR limit | 180 bpm | 180 bpm |
| HVR counter | 8 events | 8 events |
| Home Monitoring** | ON | ON |
| Time of transmission*** | 01:00 am | 01:00 am |
| Periodic IEGM*** | 30 days | 30 days |
| High Atrial Rate*** | AT | AT |
| Ongoing Atrial Episode*** | 12 h | 12 h |
| High Ventricular Rate*** | ON | ON |

* In the investigational devices, the pacing OFF mode can be normally programmed only temporarily for diagnosis purpose. However it can be made permanent in this study by releasing a special code in the programming software.

** Recommended value. The parameter can be modified if necessary. Different settings are not considered protocol deviations.

*** If HM is activated.

9.4.1 ODO mode programming

The ODO mode can be activated by selecting "OFF" in the "Modes" window. In standard operating conditions, pacing OFF is a temporary function: it is active until the programming head is applied or the radiofrequency telemetry connection (SafeSync®) is enabled. This is indicated by a "Conflict" symbol and explained by the text "*The OFF mode is only intended for diagnostic purposes during follow-up. Therefore it can only be temporarily programmed*", appearing on the programmer display when clicking on the "Conflict" button, once the OFF program is enabled. When the programming head is removed or the SafeSync® telemetry is disabled, the OFF program is cancelled and the latest pacing mode is restored.

In order to activate the OFF mode permanently, a special code will be required by the programmer software. To release the code the user must access the "Release" tab under the "More" menu of the programming device. The password/code is communicated only to hospital staff involved in the study after appropriate training.

A "Conflict" symbol will still be displayed on the programmer screen. The OFF program will then be permanently active even after the programming head removal or the radiofrequency connection interruption.

9.4.2 AV Delay programming

The AV Delay programming should favor the intrinsic conduction as much as possible.

In addition, in patients in the active group (DDD-CLS) the AV Delay should be programmed to ensure that both during spontaneous and paced atrial rhythms, the intrinsic AV conduction always occurs at least 80 ms earlier than the programmed ventricular pace.

9.4.3 Patient's Questionnaire

At enrolment or at post-implant hospital discharge, enrolled patients will be provided with a questionnaire for self-reporting of syncopal recurrences and syncope/pre-syncope-related symptoms.

Patients must be thoroughly instructed on the scope of the diary and when and how it must be filled in.

9.5 In-hospital follow-up visits

9.5.1 1-month in-hospital visit (optional)

A 1-month follow-up may take place 30 ± 14 days after post-implant hospital discharge, in order to repeat a TT and assess the effect of pacing therapy on TT response. This additional visit is optional and the decision on whether or not to perform it, is left to Investigator's discretion. If performed, the procedures described below should be followed.

Before performing the TT, the following procedures should be performed, in order to assess the correct functioning of the pacing system:

- Interrogate the IPG and document (print or save electronically) all the manually or automatically measured results of the P/R-wave amplitude, threshold, impedance tests.
- Document and assess any spontaneous high atrial or ventricular rate episode, by electronically saving or printing the relative IEGM (whenever available) occurred since the last interrogation.
- Check the activation of required and recommended parameter settings (see Table 3). In case the CLS function is not active in a subject randomized to the Active group, immediately activate the CLS and do not perform the TT immediately. Reschedule another appointment 24 hours later or as soon as possible thereafter.
- Report any adverse event or device deficiency. In case of a serious adverse event, please provide the information immediately to BIOTRONIK, and inform the ethical committee and competent authority, if required.
- Interrogate and store the final programmed parameters.
- Perform the TT as reported in next subsection.
- Schedule the next in-hospital visit within the allowed time windows.
- Complete the appropriate eCRF. Store IPG data of the programmer (Renamic) on USB flash drive and send it via email to the project management.

9.5.2 Tilt Test procedure at 1-month in-hospital follow-up (optional)

The same device programming assigned by the randomization must be maintained throughout the TT: patients randomized to the Active arm will perform TT in DDD-CLS mode and patients randomized to the Control arm will perform TT in ODO mode.

A pacemaker programmer must be available in the room and switched on before the test starts. TT will be performed according to the Italian protocol⁽⁷⁾. Electrocardiogram and systolic and diastolic BP will be continuously monitored and recorded using an external device (see Section 4.3). After 10 min of supine rest, the patients will be tilted to 70° using an electronically operating tilt-table with a footboard. If syncope will not occur after 20 min, 300 mg of nitroglycerin will be administered sublingually, and the test continued for a further 20 min or until syncope occurrence.

TT response includes: time of onset of DDD pacing and its duration, BP value at the time of onset of DDD pacing, time of onset of pre-syncope (as defined in the section 7.1.2.1), BP value at the time of onset of pre-syncope, occurrence and time of onset of syncope, type and duration of asystole, minimum BP. ECG strip of the event must be collected.

In case of device interrogation, the following procedures should be performed:

- During the device interrogation an emergency equipment for resuscitation must be kept at hand and properly certified staff must be available.
- Continuously monitor the patient's hemodynamics during the entire device interrogation using at least one of the following parameters: blood oxygen saturation, blood pressure or ECG.

9.5.3 In hospital follow-ups at 12 and 24 months

Routine in-hospital follow-up visits will occur 12 and 24 months after post-implant hospital discharge, within a ± 30 days interval, in order to check for the correct functioning of the pacing system. More frequent visits should be documented.

The following procedures should be performed:

- During the device interrogation an emergency equipment for resuscitation must be kept at hand and properly certified staff must be available.
- Continuously monitor the patient's hemodynamics during the entire device interrogation using at least one of the following parameters: blood oxygen saturation, blood pressure or ECG.
- Interrogate the IPG and document (print or save electronically) all the manually or automatically measured results of the P/R-wave amplitude, threshold, impedance tests.
- Document and assess any spontaneous high atrial or ventricular rate episode, by electronically saving or printing the relative IEGM (whenever available) occurred since the last interrogation.
- Check the activation of required and recommended parameter settings (see Table 3).
- Report any adverse event or device deficiency. In case of a serious adverse event, please provide the information immediately to BIOTRONIK, and inform the ethical committee and competent authority, if required.
- Interrogate and store the final programmed parameters.
- Schedule the next in-hospital visit within the allowed time windows.
- Complete the appropriate eCRF. Store IPG data of the programmer (Renamic) on USB flash drive and send it via email to the project management.

9.5.4 Interim follow-up

Unscheduled interim follow-up may occur anytime during the course of the study. No specific study procedures are required for interim follow-up.

If any adverse events or device deficiencies occurred, they must be documented on the respective eCRFs.

In case of device interrogation, the following procedures should be performed:

- During the device interrogation an emergency equipment for resuscitation must be kept at hand and properly certified staff must be available.
- Continuously monitor the patient's hemodynamics during the entire device interrogation using at least one of the following parameters: blood oxygen saturation, blood pressure or ECG.

9.5.5 Study termination

Should the dropout criterion (section 8.8.5) or a termination criterion (section 8.8.6) be met for a patient, a follow-up must be performed. This follow-up can coincide with one of the scheduled study follow-ups. If the patient's pacemaker was programmed in ODO mode, this must be deactivated (see section 9.5.5.1) and a different pacing mode must be programmed. The physician is responsible for the correctness and appropriateness of the pacemaker programming after this follow-up. The programmer printout of the follow-up must be filed in the Investigator Site File for source data verification.

9.5.5.1 ODO mode disabling

As any other pacing mode, the OFF program may be disabled by applying the programming head (or enabling the SafeSync® telemetry), interrogating the device with the programmer and selecting and transmitting a different pacing mode.

9.6 Primary endpoint collection

Self-administered anonymous patient questionnaires will be collected every 3 months after post-implant hospital discharge (within a ± 14 day interval) by independent personnel of a CRO as described in section 8.3.3.

Syncope and pre-syncope assessment will be exclusively based on what patients will refer by self-administering the questionnaire, at home, separately for each event.

Despite patients will be instructed to fill in the study questionnaire, they might react differently to a syncope recurrence during the study. The following Table 4 reports the most awaited situations and illustrates the subsequent steps accordingly.

Table 4. After a syncopal and pre-syncopal recurrence

| Situation: | The patient fills in the questionnaire | The patient shows up for a medical examination |
|------------|---|---|
| 1 step | The CRO quarterly collects patient questionnaires | The investigator recommends the patient to mail the questionnaire to the CRO in due time and reports any AE |
| 2 step | If an AE occurred, the CRO informs the investigator | |

Any change of the programmed pacing mode not justified by a primary endpoint (even when a-posteriori assessed), will be considered as a crossover, but analyzed according to the Intention-To-Treat (ITT) principle, see Section 11)

9.7 Description of the activities performed by sponsor representative

Sponsor representatives may support the investigator by conducting lead and device based measurements at IPG implant or in-hospital visits. They might also support the investigator for IPG programming.

During follow-up procedures, sponsor's representatives might support the interrogation of the IPG or memory dump download as needed. Monitoring will be performed by Sponsor representatives or delegated CRO personnel according to the monitoring plan.

9.8 Responsibilities of the coordinating clinical investigator and the Steering Committee

The BIOSync CLS clinical study is coordinated by:

Dr. med. [name]
Arrhythmologic Centre
Department of Cardiology
Ospedali del Tigullio
[name]
[name]
Italy

Dr. med. [name] will co-chair the Steering Committee.

The Steering Committee will consist of a local study coordinator in participating country with a sufficient number of active investigational sites.

The CCI ([name]) and the co-CCI ([name]) will be supported in the following activities by the Steering Committee.

The responsibilities of the CCI and the Steering Committee are:

- Development and review of the clinical investigation plan
- Procurement of the central vote of an ethics committee (CCI)
- Performance and progress control of the study
- Continuous assessment of the risk/benefit ratio
- If necessary, decision on premature study termination in consultation with the sponsor
- Contribution to coordination of publication and presentations of study results
- Advising all investigators in medical questions related to the study or study conduction
- Evaluation of potential unexpected adverse events
- Discussion of possible interim results
- Cooperation in writing of the final clinical report

The CCI and the Steering Committee are supported by the clinical study manager and other members of the sponsor.

In addition, the CCI and the Steering Committee members have the same rights and duties as other investigators which are described in the Investigator Agreement.

9.9 Primary and clinical secondary endpoint Adjudication Board

All the unclassified syncope or pre-syncope episodes (see section 8.3.3) will be adjudicated by an Adjudication Board of at least 3 members. The members will be selected among experienced physicians with documented expertise in syncope. The members will not participate in the study as Investigators

The Adjudication Board will review unclassified endpoint events according to a charter provided in a separate document.

The members will remain blinded to the randomization, even if they will have access to the electronic CRF.

The adjudication process will be requested by the study Project Manager after the required number of primary endpoint events for the interim analyses has exceeded the predefined levels (see section 11.6).

The interim analyses will be performed only with the events collected at the times of the call for the adjudication from the Project Manager. Further events possibly occurring thereafter will not be included.

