6.3 Steps to control or mitigate the risks

As reported in the Risk Analysis and in the IB the following measures will be adopted to mitigate the risks associated with the participation in the study.

Clinical Investigation Plan and Study Design shall include:

- 1) An independent DSMB will be monitoring the study conduct reviewing all available source document related to any death occurring during the study and recommending early study termination, if deemed appropriate.
- 2) Should a patient in ODO mode study arm die, source document review will be performed immediately, without any undue delay as soon as all relevant documents are available
- 3) The following procedures have been introduced in the study CIP:
 - Subjects terminate study participation at the first adjudicated syncope recurrence
 - Three interim analysis are planned to early terminate the study in case of evidence of superiority of the treatment arm
 - independent DSMB to periodically monitor the study status and preliminary results, recommending termination in case of unacceptable risk
 - Investigators are allowed to take any medical decision deemed appropriate, including pacemaker reprogramming
 - Advice the patient to avoid activity which may pose risks in case of transient loss of consciousness
- 4) The password/code is communicate only to hospital staff involved in the study after appropriate training
- 5) Resuscitation equipment available during pacemaker setup
- 6) The following measures must be taken during a TT:
 - a pacemaker programmer available in the room and switched on before the test starts
 - Adherence to current guidelines
 - Use of nitroglycerine
 - Resuscitation equipment available during tests
- 7) Initial training and, if necessary, periodic re-training of the hospital study staff

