7.4 Safety assessments

All Adverse Events (AE) and Adverse Device will be reported and documented and risk analysis will be constantly updated throughout the study.

An independent DSMB will be monitoring the study conduct reviewing all available source document related to any death occurring during the study and recommending early study termination, if deemed appropriate.

Should a patient in ODO mode study arm die, source document review will be performed immediately, without any undue delay as soon as all relevant documents are available

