8.3 Measures taken to minimize or avoid bias

8.3.1 Randomization

Patients will be randomized to the active group or to placebo immediately after their enrolment and before any subsequent study-related procedure.

- Active group: before post-implant hospital discharge, IPG will be programmed in a dual-chamber DDD pacing mode with the CLS function ON, and according to the programming recommendations reported in section 9.4.
- Control group: before post-implant hospital discharge, pacing will be programmed in the ODO mode, according to the programming recommendations reported in section 9.4.

Randomization ratio will be 1:1, therefore the randomization procedure will ensure that each individual patient will have (approximately) 50% chance to be assigned to the active group or to the control.

A centralized block-randomization procedure will be used. Block size will vary from 2 to 4 and investigators will not be aware of randomization block sizes at any time. Randomization will not be stratified.

Randomization will be communicated with an online procedure: investigators will connect to a dedicated webpage of the electronic Case Report Form (eCRF).

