8.4 Methods

8.4.1 eCRF

All parameters and measurements that are recorded within the study are described in this section and are documented on the appropriate eCRFs.

The corresponding time schedule is described in Section 9.

- Enrollment Form
- Baseline Form
- Implantation Form
- Pre-Hospital Discharge Form
- In-hospital Follow-up Form for 1- (optional), 12-, 24-month follow-up visits, as well as interim visits.
- Patient's self-administered questionnaire
- Adverse Event/Device Deficiency Form
- Study Termination Form

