18.11 Data safety monitoring committee

The Data Safety Monitoring board will consist of the same members of the Endpoint Adjudication Board (see section 9.9).

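### The Adjudication Board is declared blinded, but it has eCRF access and is the same panel as the DSMB, and nothing in the supplied text secures that blinding

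*Protocol*

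**What the plan says.** **The Board's task.** Protocol section 9.9: "All the unclassified syncope or pre-syncope episodes (see section 8.3.3) will be adjudicated by an Adjudication Board of at least 3 members". Episodes that the questionnaire answers settle do not go to the Board (8.3.2, 8.3.3). Board members may not be study investigators, and they work to a charter kept as a separate document.

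**Its blinding.** The same section states: "The members will remain blinded to the randomization, even if they will have access to the electronic CRF". It adds nothing on how this is achieved.

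**What the eCRF holds.** Section 8.4: "All parameters and measurements that are recorded within the study are described in this section and are documented on the appropriate eCRFs". The forms listed there include the pre-discharge and in-hospital follow-up forms. Table 2 schedules "Device programming settings and diagnostics" at discharge, at the optional month-1 visit, and at months 12 and 24. Table 3 (section 9.4) sets the mode to DDD-CLS in the active group and OFF in the control group. Under 8.3.1 the investigator obtains the allocation itself on a page of the eCRF.

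**The second role.** Section 18.11: "The Data Safety Monitoring board will consist of the same members of the Endpoint Adjudication Board". Section 6.3 lists among the safeguards an "independent DSMB to periodically monitor the study status and preliminary results", with the power to recommend termination. Section 7.4 adds: "Should a patient in ODO mode study arm die, source document review will be performed immediately".

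**The SAP.** Section 7.5 bases double-blinding of endpoint assessment on collection of the questionnaires by external CRO personnel. For the process it refers to the charter and to a figure that is missing from the text supplied.

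**The concern.** Two routes could bring the arm to a Board member. The first is the patient's own record: one programming field tells DDD-CLS from OFF. The second is the DSMB role, which requires at least the arm of any patient who dies in ODO mode and may involve more.

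Unclassified episodes are the ones where judgement decides. Section 7 of the protocol expects CLS to work partly by turning syncope into pre-syncope. The Board's call between the two therefore falls on the primary endpoint boundary, at the place where treatment is expected to act. Section 3.1 itself warns that syncope studies are open to bias when blinding is missing. If the Board knew the arm, the double-blind claim would have a gap at the primary result, and classifications already made could not be blinded afterwards.

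**Working it through.** **1. Is a safeguard stated anywhere?**
- Section 9.9 requires blinding but gives no mechanism.
- Section 12.2 says database users have fixed roles. It describes reading, entering, updating, resolving queries and signing, and does not say that any form is hidden from the Board.
- Section 20.2 names patients and CRO personnel as blinded and does not mention the Board.
- SAP 7.5 describes the protection at questionnaire collection.
- No rule in 9.9, 11.7.1 or 18.11 orders the Board's classifications relative to what its members see as DSMB.

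The supplied text therefore leaves the route to the arm open without showing that it is used.

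**2. The plan's own figure.** With a two-sided alpha of 0.05, 80% power, 1:1 allocation and HR 0.49:

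events = (1.960 + 0.842)² / (0.25 × ln(0.49)²) = 7.849 / 0.1272 = 61.7, rounded up to 62.

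The stated 62 is reproduced. It needs the square on log(HR), which the printed formula lacks. The boundaries 3.3569, 2.4445 and 2.0005 return an overall two-sided alpha of 0.0500. The tail beyond 2.0005 in favour of CLS is 0.023, which is the reference value below.

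**3. Illustration of size (assumptions, not document figures).** Suppose no true effect, 62 events and only the final look. A share u of candidate episodes goes to the Board, which confirms a fraction c_ctl in control and c_cls in CLS. Both u and the confirmation rates are assumed.

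- Apparent HR = [(1 − u) + u × c_cls] / [(1 − u) + u × c_ctl]
- Shift in Z = |ln HR| × √(62/4)
- False finding for CLS = 1 − Φ(2.0005 − shift)

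Example, u = 0.20 with 75% versus 25%: HR = 0.85/0.95 = 0.895; shift = 0.111 × 3.937 = 0.438; probability = 1 − Φ(1.563) = 0.059.

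| Share to Board | 60% vs 40% | 75% vs 25% | 100% vs 0% |
|---|---|---|---|
| 5% | 0.0250 | 0.0287 | 0.0360 |
| 10% | 0.0276 | 0.0365 | 0.0564 |
| 20% | 0.0340 | 0.0591 | 0.1309 |
| 30% | 0.0425 | 0.0961 | 0.2755 |

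Confirmation rates are control versus CLS.

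**4. How much the model matters.** A cruder calculation applies the tilt to the 2-year incidence and treats a rejected episode as lasting freedom from syncope. With 57% reported in both arms, a 30% share, and confirmation of 90% in control against 50% in CLS:

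- control: 0.57 × (0.7 + 0.3 × 0.9) = 0.553
- CLS: 0.57 × (0.7 + 0.3 × 0.5) = 0.485
- HR = ln(1 − 0.485) / ln(1 − 0.553) = 0.82

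Patients with a rejected episode in fact stay in the study (8.8.6). If half of them later have a classified event, an assumption again, the fractions become 0.7 + 0.3 × 0.95 = 0.985 and 0.7 + 0.3 × 0.75 = 0.925, and the HR moves to 0.91.

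**The case against.** The case on the other side is substantial.

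- **Blinding is a stated requirement.** Section 9.9 anticipates the tension and still demands blinding. Section 12.2 provides role-based access, so a Board login that hides the arm is feasible. The randomisation page in 8.3.1 is described for investigators, not for the Board.
- **The governing document is unseen.** The content of the Board's dossier would naturally be set in the charter cited in 9.9 and SAP 7.5.
- **The DSMB material may not be comparative.** No text says that preliminary results are shown by arm. The planned comparative interim analyses are run by an independent statistician and reported to the coordinating investigator and the sponsor (11.7.1); the DSMB is not named as a recipient. The ODO-death rule discloses the arm of a patient who has died, not of living patients whose episodes await classification.
- **The sequence helps in part.** Adjudication is called in batches before each interim analysis (9.9, 11.7.1), so the first batch is classified before any planned comparison exists.

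Most of this stands, and it limits the point. A reader might infer that blinding cannot hold, or that any member who opens a record sees the arm. The documents do not support that, because the forms open to a Board login are not specified. A reader might also infer that the Board knows how the arms are trending. No passage says so.

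What remains is that the supplied text grants eCRF access and shared membership without a masking or sequencing rule. The batch order protects only the first batch, and only from planned interim results, not from the patient record.

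**Conclusion.** The point holds as an unsecured safeguard: the arm can become known to the Board, and nothing supplied shows that it will be. The reach is limited to unclassified episodes, whose share the documents do not give.

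The size is illustrative only. If few episodes go to the Board, the effect on the false-positive rate is small. It becomes material at a share of about 20% or more combined with a strong tilt by arm: 0.059 to 0.096 against 0.023 at 75% versus 25%. With a mild tilt it stays near 0.04 or below throughout. These figures rest on the assumed shares and confirmation rates, on no true effect, and on the final look alone.

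Should-fix, with moderate confidence. If the charter already masks the Board and orders its two roles, stating this in 9.9 and 18.11 settles the matter.

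**What to change.** - **Section 9.9:** replace general eCRF access with a restricted database role, or with a redacted packet holding the questionnaire and the clinical narrative. Either should exclude randomisation, programming, pacing, IEGM and Home Monitoring data.
- **Section 18.11:** require the Board to lock its classification of all episodes up to a data cut before members see any arm-identifying DSMB data. Show any DSMB tables by coded arm. Because the death review in 7.4 is immediate, a member who took part in it should not then classify that patient's episodes. Separate membership would be cleaner, but the fix does not depend on it.
- **SAP 7.5:** report the number of Board-adjudicated events by arm, and add a sensitivity analysis of the primary endpoint that excludes them.
- **Charter:** check it first and align it with these rules.

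The cost is a change of user rights in a system that already uses roles, a charter edit, redaction of what should be a small number of packets, and one extra analysis. The downside is that the Board loses the full record. Treatment, sample size and the primary analysis do not change.
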